This study will be a single-blinded prospective randomized trial in pediatric patients undergoing minor urologic surgery. Pediatric patients will be randomized in a 1:1 fashion to receive dorsal penile nerve block (circumcision, hypospadias repair, penile cyst excision, meatoplasty, chordeolysis) or spermatic cord block with local wound infiltration (orchiopexy, orchiectomy, inguinal hernia, hydrocelectomy, varicocelectomy) with Exparel® plus 0.25% Bupivacaine versus standard 0.25% Bupivacaine alone. Patient families will also be cross randomized in a 1:1 fashion to receive standard post-operative pain instructions, with or without opioid disposal instructions. Families that consent to participation in the trial will be informed of randomization to Exparel® plus 0.25% Bupivacaine versus standard 0.25% Bupivacaine but will be blinded to arm assignment. Families will also be informed that they will be receiving postoperative pain instructions, however they will not be informed of whether or not they receive opioid disposal instructions.

No other standard pre-, peri- or post-operative pediatric urologic surgery procedures will be affected. Routine care includes an initial clinic consultation, physical examination, and informed consent prior to proceeding with surgery. Informed consent for participation in the study may also be obtained in the preoperative area during the day of surgery. Eligibility will be confirmed at the time of consent. Patient will be randomized after consent is obtained and appropriate postoperative pain instructions with or without opioid disposal instructions will be given at that time to minimize drop out.

Anesthesia team will be notified when local wound infiltration or penile nerve block is being performed as is standard operating procedure, however we will not dictate what other intra or peri-operative analgesia is given. All blocks will be performed by the surgical team using landmark techniques.

Patients will be given the option of returning to the Johns Hopkins clinic or local follow-up (with a provider) for wound check approximately 7-14 days after surgery.

[figure not shown]

Figure 1. Diagram of plan for stratified randomization of patients to arms and outcomes assessed.

Date: 12/1/2021

Principal Investigator: [name] [name]

Application Number: IRB00284462

ClinicalTrial.gov Identifier: NCT04826484

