- b. If your study involves data/biospecimens from participants enrolled under other research studies with a written consent or under a waiver of consent, please list the IRB application numbers for those studies. Please note: Certificate of Confidentiality (CoC) protections applied to the data in source studies funded by NIH or CDC will extend to this new study if the funding was active in 2016. If this situation applies, Section 36, question 6 in the application will need to be answered “Yes” and “Hopkins Faculty” should be selected in question 7. No other documents are required.

N/A

- c. Study duration and number of study visits required of research participants.

The study protocol will be implemented during routine visits and minor pediatric urologic surgery. This includes patients undergoing orchiopexy, orchiectomy, circumcision (primary and revision), distal hypospadias repair, meatotomy/meatoplasty, chordee repair, penile cyst excision, urethrocutaneous fistula repair, inguinal hernia repair, hydrocelectomy, and varicocelectomy. Patient will receive normal postoperative follow up for a wound check and will receive phone correspondence at 48 hours and 10-14 days postoperatively to collect data regarding opioid prescribing, opioid use, pain, and disposal.

- d. Blinding, including justification for blinding or not blinding the trial, if applicable.

Pediatric randomized in a 1:1 fashion to receive dorsal penile nerve block or spermatic cord block with local wound infiltration with Exparel® plus 0.25% Bupivacaine versus standard 0.25% Bupivacaine. Families will consent to enrollment in the trial to receive either Exparel® plus 0.25% Bupivacaine or standard Bupivacaine but will remain blinded to which local anesthetic is given intraoperative to ensure there is no bias between arms with respect to opioid administration or postoperative pain expectations by the family. Consent for the trial will be performed by the study coordinator and surgeons will not be aware of treatment allocation until patient is in the operating room and block is ready to be administered.

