4. Unwilling or unable to participate in 48 hours and 10-14 day follow-up phone calls

6. Drugs/ Substances/ Devices

- a. The rationale for choosing the drug and dose or for choosing the device to be used.

Exparel® is composed of a liposomal bupivacaine formulation that allows retention of local anesthetic at the site of injection to allow for durations as long as 72 hours.¹² To date, no other long lasting non-opioid pain control exists for pediatric patients undergoing surgery.

Date: 12/1/2021

Principal Investigator: [name] [name]

Application Number: IRB00284462

ClinicalTrial.gov Identifier: NCT04826484

Per the Exparel® dosing and administration guide, the maximum recommended dose for Exparel® is 4 mg/kg. Bupivacaine may be given concurrently with Exparel as long as the ratio of the milligram dose of bupivacaine HCl to Exparel does not exceed 1:2 (50% of the mg dose of Exparel).¹² Each Exparel® contains 133 mg of liposomal bupivacaine in 10 ml saline, or 13.3 mg/ml. 0.25% bupivacaine contains 2.5 mg/ml of bupivacaine. Patients randomized to the intervention arm received sequential weight-based administration of 0.5 mg/kg (maximum recommended dose 2.5 mg/kg) of 0.25% bupivacaine hydrochloride without epinephrine followed by 2.5 mg/kg (maximum recommended dose 4 mg/kg) of 1.33% liposomal bupivacaine such that the ratio of the milligram dose of bupivacaine hydrochloride to liposomal bupivacaine did not exceed 1:2 (50% of the mg dose of liposomal bupivacaine) as described in the medication dosing insert.

- b. Justification and safety information if FDA approved drugs will be administered for non-FDA approved indications or if doses or routes of administration or participant populations are changed.

Exparel® is an FDA-approved non-opioid local anesthetic that is approved for single-dose infiltration to produce post-surgical local anesthesia for pediatric patients six years and older.¹²

- c. Justification and safety information if non-FDA approved drugs without an IND will be administered.

N/A

7. Study Statistics

- a. Primary outcome variable.

The primary efficacy endpoints will be the percentage of pediatric patients who are opiate-free at 48 hours and at 10-14 days postoperatively, parents' postoperative pain measure (PPPM) scores at 48 hours and 10-14 days postoperatively, amount of opioid used following discharge (as measured by weight based oral morphine equivalents), and the amount of opioid leftover at 10-14 days.

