28% to 50%: n = 152; 76 in each arm

28% to 40%: n = 486; 243 in each arm

28% of peds uro pts from recent JHH anesthesia study required zero opiates

Consensus among the study investigators suggested that a 50% opioid-free rate at 48 hours (22% absolute difference between arms) would be the minimal clinically relevant difference in the primary outcome measure.

Assuming a 25% rate of lost-to-follow-up or incomplete follow-up data, we will plan to enroll 100 pediatric patients per arm, or 200 patients total. Target enrollment may be subject to change if the lost to follow-up rate is significantly higher or lower than 25%.

Randomization lists will be generated by the study coordinator. The investigators will maintain the randomization list, password protected, on a remote drive maintained by the Department of Urology and will provide the random assignment to the study coordinator as each patient is enrolled.

One interim analysis of the primary efficacy and primary safety endpoint will be planned with potential early stopping for efficacy or futility. The interim analysis will be conducted after half

Date: 12/1/2021

Principal Investigator: [name] [name]

Application Number: IRB00284462

ClinicalTrial.gov Identifier: NCT04826484

of the patients have been enrolled. O'Brien-Fleming boundaries will be used, as implemented in PASS v. 11 (NCSS Software, Inc., Kaysville, UT).

One interim analysis of the primary efficacy endpoint will be conducted after information proportion of 0.66 (n = 102) to assess for early stopping for efficacy or futility. The total sample size needed for 80% power with a 1-sided test was 152 patients (76 per arm), based on 10,000 simulations. Alpha-spending at the interim analysis and final analysis was 0.016 and 0.034 (cumulative alpha spent 0.016, 0.05), respectively. The futility boundaries at the interim analysis and final analysis were p=0.24 and p=0.048, respectively. At the interim analysis the rates of all-cause surgical complications and those attributable to sequela of the local anesthetics or symptoms related to LAST were also evaluated. An unacceptable rate of all-cause surgical complications was >10%. If the lower 95% confidence bounds met or exceeded this rate for all-cause complications or there were any episodes of LAST, the trial would have been halted for further review and consideration of early stopping.

Statistical Analysis

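### The study coordinator both generates the randomisation list and obtains consent, with no stated separation, so allocation is not assured to be concealed from the recruiter

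*Combined protocol and SAP*

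**What the plan says.** Section 7c (statistical plan) assigns generation of the sequence: "Randomization lists will be generated by the study coordinator". It then describes custody and release: "The investigators will maintain the randomization list, password protected, on a remote drive maintained by the Department of Urology", and the investigators "will provide the random assignment to the study coordinator as each patient is enrolled".

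Section 4d (blinding) assigns recruitment to the same role: "Consent for the trial will be performed by the study coordinator and surgeons will not be aware of treatment allocation" until the patient is in the operating room and the block is ready. It makes no matching statement about the coordinator.

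Section 4a sets the order of steps: "Eligibility will be confirmed at the time of consent" and "Patient will be randomized after consent is obtained". It does not say who confirms eligibility. One exclusion in section 5 calls for some judgement: "Unwilling or unable to participate in 48 hours and 10-14 day follow-up phone calls".

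Section 8c allows for more than one research coordinator, but only when describing how problems are reported. It does not divide duties.

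**The concern.** Randomisation protects against selection only if the person deciding whom to approach and enrol cannot foresee the next assignment. As written, one role creates the sequence and then recruits against it. A coordinator who kept a copy, or remembered part of the order, could influence, even unintentionally, which families are approached or judged able to take the follow-up calls. The arms could then differ before any drug is given.

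The main comparison is the opioid-free rate at 48 hours, collected from families by phone. Parental anxiety and attitudes to opioids could plausibly affect both recruitment and that outcome. The logistic regression planned under Statistical Analysis can adjust for measured imbalances such as age or surgery type, but not for factors that nobody recorded. Intention-to-treat analysis does not undo selection that took place before randomisation.

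**Working it through.** **Roles side by side**

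| Step | Who | Section |
|---|---|---|
| Generate the list | Study coordinator | 7c |
| Hold the list | Investigators, password protected | 7c |
| Obtain consent | Study coordinator | 4d |
| Confirm eligibility | Not stated; at time of consent | 4a |
| Release each assignment | Investigators to study coordinator | 7c |
| Stated to be unaware of allocation beforehand | Surgeons only | 4d |

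One-at-a-time release shows that the coordinator is meant to learn each assignment only at enrolment. Giving the coordinator the task of generating the list works against that intention. No section says that the two tasks fall to different people, or that the generator keeps no copy.

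**The plan's own sample size (context only)**

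For 28% against 50%, two-sided 0.05 and 80% power, the mean rate is 0.39:

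n = [1.960 × √(2 × 0.39 × 0.61) + 0.842 × √(0.28 × 0.72 + 0.50 × 0.50)]² / 0.22² = 75.97, or 76 per arm, as section 7c states.

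The concern does not dispute this figure.

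**How large a bias could be (assumed figures)**

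The documents give no basis for an estimate, so this is an illustration only. Assume two equal prognostic groups averaging the protocol's 28%, separated by a gap g on an unmeasured factor. A share m of the Exparel arm, and 1 − m of the control arm, comes from the better group. With no drug effect:

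- Spurious difference = g × (2m − 1).
- Larger case, g = 0.20 and m = 0.60: group rates are 0.38 and 0.18. Exparel is 0.6 × 0.38 + 0.4 × 0.18 = 0.30 and control is 0.4 × 0.38 + 0.6 × 0.18 = 0.26. The difference is 0.04, and 0.04 / 0.22 = 18% of the target effect.
- Smaller case, g = 0.10 and m = 0.55: 0.285 against 0.275, a difference of 0.01.

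The probability of a significant result favouring Exparel was found by exact binomial enumeration (76 per arm, uncorrected pooled chi-squared test, single look, interim analysis ignored):

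| Case | Two-sided 0.05 | One-sided 0.05 |
|---|---|---|
| No selection | 0.0248 | 0.0487 |
| Larger case | 0.0783 | 0.1336 |
| Larger case, steering reversed | 0.0060 | 0.0137 |
| Smaller case | 0.0339 | not run |
| Smaller case, steering reversed | 0.0178 | not run |

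Both kinds of test are shown because section 7c describes both.

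**How unusual such mixes are by chance**

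The standard error of a difference in mix at 76 per arm is √(2 × 0.25 / 76) = 0.081. The larger case (60/40 against 40/60) is 0.20 / 0.081 = 2.5 standard errors, so it needs consistent steering. The smaller case (55/45 against 45/55) is 0.10 / 0.081 = 1.2 standard errors.

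**The case against.** The best defence is that the plan already addresses concealment. Custody by the investigators, sequential release and randomisation after consent make sense only if the coordinator is not supposed to see ahead. Recalling a sequence for 200 patients is implausible when the randomisation is stratified (Figure 1 caption) and crossed with a second allocation to disposal instructions. The realistic route is therefore a retained copy, which the documents do not mention. Figure 1 is not shown, so any procedural detail in it cannot be checked.

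Discretion is also limited. Age and contraindications are fairly objective, and willingness to take the calls depends largely on the family's own answer. Section 7c implies about 100 potentially eligible procedures a year (20% of 500) against a target of 200 patients, so passing over families would slow recruitment noticeably. Finally, the illustration rests on assumed inputs. In the smaller case the total two-sided error rate barely moves, from 2 × 0.0248 = 4.96% to 0.0339 + 0.0178 = 5.17%.

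These are fair points about weight. They make memory an unlikely route and show that no firm size can be given. They do not supply the missing separation: password custody after handover cannot conceal a list from its author, and slower recruitment does not rule out selective approach. That the coordinator may be more than one person is possible, but the plan does not say so.

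**Conclusion.** The concern holds. The plan states a procedure in which one role generates the list and recruits against it, and its controls do not close that gap. This should be fixed. It is a weakness in the stated procedure, not evidence that concealment failed.

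Any bias cannot be sized from the documents. On the assumptions above, the chance of a false result favouring Exparel ranges from 3.4% to 7.8% against a nominal 2.5%, and falls below nominal if steering runs the other way. The conclusion rests on the overlap of roles, not on these figures. It would fall away if two different people perform the tasks and the recruiting one has no access to the list.

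One related point needs clarifying and is not a shown defect: the documents do not say whether any investigator holding the list also operates. That bears on the statement in section 4d that surgeons are unaware of allocation until the block is ready.

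**What to change.** In section 7c:

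- State that the list is generated by someone who neither consents patients nor operates, or by an electronic randomisation system.
- State that each assignment is released only after eligibility and consent have been recorded.
- State that neither the consenting coordinator nor any operating surgeon can see upcoming assignments, and clarify whether any investigator holding the list operates.
- If separate coordinators already generate the list and obtain consent, say so, and state that the recruiting one has no access to it.

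Parts of sections 6a and 7c are in the past tense (for example, "Patients randomized to the intervention arm received sequential weight-based administration"), so enrolment may already have begun. In that case, document who generated the list and who had access to it, and report any overlap with recruitment as a limitation. No later analysis can restore concealment.

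The cost is a small set-up effort and a change of access to the list, or documentation only if enrolment is under way. Patient procedures, sample size and analysis are unchanged. The documents do not say who is available to take on the role.

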The primary safety endpoints will be the incidence of pre-defined complications related to local anesthetic systemic toxicity (exceedingly rare in all phase 2 and 3 trials), and the percentage of families properly disposing of leftover opiate medication at 10-14 days postoperatively.

The primary analysis will involve two separate comparisons: 1) Comparison of primary efficacy endpoints between those receiving Exparel® plus 0.25% Bupivacaine versus those receiving standard 0.25% Bupivacaine alone, and 2) Comparison of primary safety endpoints between those receiving Exparel® plus 0.25% Bupivacaine versus those receiving standard 0.25% Bupivacaine alone.

- b. Secondary outcome variables.

Date: 12/1/2021

Principal Investigator: [name] [name]

Application Number: IRB00284462

ClinicalTrial.gov Identifier: NCT04826484

Secondary outcomes will include a cost comparison of Exparel® plus 0.25% Bupivacaine versus standard 0.25% Bupivacaine alone, as well as evaluating efficacy of using Exparel® for a penile nerve block versus incisional infiltration with regard to safety and efficacy.

c. Statistical plan including sample size justification and interim data analysis.

All patients that meet inclusion criteria for the trial and are consented will undergo cross-randomization (Figure 1) to receive either 0.25% Bupivacaine or Exparel® plus 0.25% Bupivacaine, opioid medication instructions with disposal instructions, or opioid medication instructions without disposal instructions.

Currently at Johns Hopkins, we perform over 500 minor pediatric urologic procedures per year, roughly 20% of which involve patients 6 years or older and could be eligible for inclusion.

We assumed that the smallest detectable difference in the primary endpoints may be the percentage of patients who are opiate-free at 48 hours and thus planned to base our power calculation on detecting a difference in this variable. Prior studies from our institution have demonstrated that roughly 28% of pediatric patients undergoing minor urologic procedures and receiving standard Bupivacaine local wound infiltration require zero opioids postoperatively.² This study will be conducted with a superiority design (does penile block or wound infiltration with Exparel® plus 0.25% Bupivacaine offer a superior opiate-free rate at 48 hours than standard Bupivacaine?).

Power of 80% (beta = 0.2) and two-sided alpha of 0.05 for increasing opiate-free rate

28% to 60%: n = 74; 37 in each arm

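### Surgeon masking has no stated mechanism: investigators keep the full randomisation list with no bar on operating surgeons, and the coordinator who generates it also obtains consent

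*Combined protocol and SAP*

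**What the plan says.** Section 7c (statistical plan) sets out the custody of the list in two sentences. On origin: "Randomization lists will be generated by the study coordinator". On storage: "The investigators will maintain the randomization list, password protected, on a remote drive maintained by the Department of Urology". On release, the investigators "will provide the random assignment to the study coordinator as each patient is enrolled".

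Section 4d (blinding) says "Consent for the trial will be performed by the study coordinator" and that "surgeons will not be aware of treatment allocation until patient is in the operating room and block is ready to be administered".

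Section 4a (study design) gives the timing: "Patient will be randomized after consent is obtained and appropriate postoperative pain instructions with or without opioid disposal instructions will be given at that time". It allows trial consent on the day of surgery as an additional option, so consent can also come earlier. It also says who gives the block: "All blocks will be performed by the surgical team using landmark techniques".

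On whether investigators operate, the nearest text is in 7c: "Currently at Johns Hopkins, we perform over 500 minor pediatric urologic procedures per year".

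No section says which investigators have the password, whether any of them operates on trial patients, or who schedules cases. The text mentions no independent custodian, sealed envelopes, pharmacy release or central system.

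**The concern.** Section 4d makes a specific claim about what surgeons know and when. For that to hold, something must stand between the list and the people who operate. Section 7c names only a password, and a password does not hide the list from those who maintain it.

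Anyone who can read the next assignments and also influences enrolment could affect which child is put forward, when, and whether a borderline child is judged eligible. Some criteria in section 5 leave room for judgement, such as a history of pain syndromes or willingness to take the follow-up calls. Recruitment is also slow enough to match a coming assignment to an identifiable child: 20% of about 500 procedures is about 100 candidates a year, or roughly two a week. Selection of this kind can shift the 48-hour opioid-free rate between arms with no drug effect.

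**Working it through.** **Step 1. Set the roles side by side.**

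| Step | Who | Section |
|---|---|---|
| Generates the list | Study coordinator | 7c |
| Obtains consent | Study coordinator | 4d |
| Confirms eligibility | Not named; done at consent | 4a |
| Holds the full list | Investigators | 7c |
| Releases each assignment | Investigators, to the coordinator, at enrolment | 7c |
| Schedules surgery | Not stated | – |
| Gives the block | Surgical team | 4a |
| Surgeon learns the arm | When the block is ready | 4d |

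- *Investigators.* 4d and 7c are compatible if nobody with access to the list operates on trial patients. They conflict if anybody with access does. The protocol does not say which case applies.
- *Coordinator.* The overlap is on the page and needs no inference: one role creates the sequence and later enrols against it.
- *Timing.* Randomisation follows consent, which can precede the day of surgery. A list-holder can therefore know a child's arm well before the block.

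**Step 2. Reproduce the plan's sizing.** Inputs from 7c: 28% v 50%, two-sided alpha 0.05, 80% power. The mean rate is 0.39.

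n per arm = [1.960 × √(2 × 0.39 × 0.61) + 0.842 × √(0.28 × 0.72 + 0.50 × 0.50)]² / 0.22² = (1.352 + 0.566)² / 0.0484 ≈ 76, as stated. Power at 76 per arm is 80.0%. List custody does not enter this figure, so the sample size is not in dispute.

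**Step 3. Illustrate sensitivity to steering.** Every steering input here is an assumption; none comes from the documents.

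- Assumed opioid-free probability: 60% for children steered to Exparel, 10% for children steered to control.
- Assumed share of slots steered: 5%, 10% or 15%, always in the direction favouring Exparel.
- Gap between arms with no drug effect: g = share × (0.60 − 0.10).
- Null standard error at 28% and 76 per arm: s0 = √(2 × 0.28 × 0.72 / 76) = 0.0728.
- s1 = standard error with rates 0.28 ± g/2, which is 0.0728, 0.0727 and 0.0726 for the three gaps.
- Chance of falsely declaring superiority = Φ((g − z × s0) / s1), with z = 1.960 (upper tail of the two-sided 0.05 test) or 1.645 (one-sided 0.05). Both are shown because 7c mentions both a two-sided alpha and a one-sided test. The interim look is ignored.

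| Share steered | Gap g | Upper tail, nominal 2.5% | One-sided, nominal 5% |
|---|---|---|---|
| 5% | 2.5 points | 5.3% | 9.6% |
| 10% | 5.0 points | 10.1% | 16.9% |
| 15% | 7.5 points | 17.5% | 26.9% |

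**The case against.** A reader might infer that the list-holding investigators are the surgeons and that upcoming arms are in plain view of those who schedule and operate. The documents do not support that. The first-person wording in 7c can mean the institution, and elsewhere surgeons and the surgical team appear in the third person (4a, 4d, 8b). Access rights and scheduling roles are not given.

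A reader might also infer that release at enrolment unmasks the surgeon. It does not: release goes to the coordinator. One-at-a-time release suggests an intention to keep the sequence from the enrolling person, and generating a list need not mean remembering it. Some limits on harm are also real:

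- Where consent is taken on the day of surgery, the operation is already booked, so that child's own assignment cannot affect booking.
- The Figure 1 caption refers to stratified randomisation and 7c to lists in the plural. The next assignment may therefore depend on the next child's stratum, and the sequence may not be one readable queue. The figure is not available in the text reviewed.
- The analysis section compares baseline factors and allows logistic adjustment.

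These points stand as limits on the claim, but they do not supply the missing safeguard. Stratified lists are still readable by someone who holds them. Adjustment reaches only measured factors, and those given as examples (age, race, BMI, comorbidities, surgery type, operative time) do not include expected opioid need. Intention-to-treat analysis preserves whatever allocation occurred. None of the points touches the coordinator's dual role.

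**Conclusion.** The concern holds in a limited form. The custody rule in 7c does not secure the masking claimed in 4d: it gives the investigators the whole list and excludes nobody who operates. The masking fails if any investigator with access also operates, which is suggested but not stated. Separately, the enrolling coordinator may know the sequence, because the same role generates it. Upcoming assignments may therefore be accessible to people who enrol or operate. A breach is not shown.

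The size of any bias cannot be derived from the documents. A reader might take the 5% to 27% range as this trial's error rate; it is not. It rests wholly on the assumed steering shares, the assumed 60% and 10% probabilities, and steering that always favours Exparel. It shows only that modest selection would matter at 76 per arm. The point is worth correcting because the remedy is cheap; sample size and analysis are unaffected.

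**What to change.** Replace the custody text in 7c with wording to this effect:

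> The list is generated and held by an existing staff member who does not obtain consent, assess eligibility, schedule or operate. Neither the consenting coordinator nor any operating investigator has access to it. The instruction-sheet assignment is released after consent. The drug assignment is released only on the day of surgery, when the block is prepared, through sealed or electronic assignments loaded in advance.

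This gives 4d a mechanism, keeps the early release of the instruction sheet that 4a needs, and closes the coordinator gap in the same edit. If no investigator with access operates, a sentence saying so would settle the surgeon part, but not the coordinator part.

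The cost is protocol wording, a change of access rights on the drive, releasing the two assignments at different times, and preparing the sealed or electronic assignments beforehand. Pre-loading avoids the need for new staff or for the custodian to be on call on operating days.

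### Section 7c gives its single interim analysis two timings, half of enrolment and information 0.66 (n = 102), which at the plan's own 25% loss lie 36 enrolled patients apart

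*Combined protocol and SAP*

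**What the plan says.** Two consecutive paragraphs of section 7c (statistical plan) each describe a single interim analysis with possible early stopping for efficacy or futility.

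- The first gives the timing as "The interim analysis will be conducted after half" "of the patients have been enrolled" (the sentence crosses a page break). It says that O'Brien-Fleming "boundaries will be used, as implemented in PASS v. 11", and prints no threshold.
- The second reads "One interim analysis of the primary efficacy endpoint will be conducted after information proportion of 0.66 (n = 102) to assess for early stopping". It adds: "The total sample size needed for 80% power with a 1-sided test was 152 patients (76 per arm), based on 10,000 simulations". It then prints the thresholds: "Alpha-spending at the interim analysis and final analysis was 0.016 and 0.034", and "The futility boundaries at the interim analysis and final analysis were p=0.24 and p=0.048, respectively".

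The sample size text in the same section sets enrolment: "Assuming a 25% rate of lost-to-follow-up or incomplete follow-up data, we will plan to enroll 100 pediatric patients per arm", 200 in total. It adds that this target may change if loss departs significantly from 25%. Section 7d requires the trial to stop if futility is met at the interim. Nothing says which timing governs, or whether 102 counts enrolled patients or patients with outcome data.

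**The concern.** The two paragraphs use different units. Half of enrolment is a share of 200, the number after the allowance for loss. The 0.66 is a share of 152, the number before it. At the plan's 25% loss they point to different moments in the trial.

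The trigger matters because the thresholds belong to a timing. An interim alpha and a futility p-value computed for about two thirds of the information do not have the same properties at about half. Section 7d also makes the futility stop mandatory, so an unclear trigger feeds a binding decision. Two written timings further leave room to choose the moment of the look after data have accrued.

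**Working it through.** **Inputs.** All are from section 7c except the 10% and 0% loss rates, which are assumptions made here: control rate 28%, target 50%, 152 patients (76 per arm), 200 enrolled, 25% loss, interim alpha 0.016, futility p = 0.24 at the interim, final p = 0.048.

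**1. The plan's sample size.** With two-sided 0.05, 80% power and no continuity correction, n per arm = [1.960·√(2·0.39·0.61) + 0.842·√(0.28·0.72 + 0.50·0.50)]² / 0.22² = 76, or 152 in total. This matches. Allowing for 25% loss, 152/0.75 = 203, close to the stated 200.

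**2. The plan's interim figures.** 0.66 × 152 = 100.3, while 102/152 = 0.671. The O'Brien-Fleming-type spending function for one-sided 0.05 is α(t) = 2[1 − Φ(1.960/√t)].

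| Evaluable | t (of 152) | α(t) |
|---|---|---|
| 75 | 0.493 | 0.0053 |
| 76 | 0.500 | 0.0056 |
| 90 | 0.592 | 0.0109 |
| 100 | 0.658 | 0.0157 |
| 100.3 | 0.660 | 0.0158 |
| 102 | 0.671 | 0.0167 |

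The printed 0.016 therefore fits 0.66 on the 152 scale, and not 0.49-0.50.

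**3. The gap in enrolled patients.** At 25% loss, 100 enrolled give 100 × 0.75 = 75 evaluable (0.49). Reaching 102 evaluable takes 102/0.75 = 136 enrolled. The gap is 136 − 100 = 36.

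At other loss rates d, the gap depends on whether enrolment stays at 200 or is reset to 152/(1 − d):

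| Loss | Enrolled for 102 evaluable | Gap, 200 fixed | Half of 152/(1 − d) | Gap, target reset |
|---|---|---|---|---|
| 25% | 136.0 | 36 | 101.3 | 35 |
| 10% (assumed) | 113.3 | 13 | 84.4 | 29 |
| 0% (assumed) | 102.0 | 2 | 76.0 | 26 |

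**4. If 102 counts enrolled patients.** 102 × 0.75 = 76.5 evaluable, and 76.5/152 = 0.50. The spend there is about 0.0056, so the printed 0.66 and 0.016 do not fit at the plan's loss rate.

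**5. Consequences.** Exact binomial calculation with the pooled z test, 28% versus 50%, 76 per arm at the end, printed p-values read as one-sided.

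*Each paragraph on its own terms, chance of an early efficacy stop:*
- Half enrolment at 25% loss (37-38 per arm), O'Brien-Fleming-type spend of 0.0050-0.0056: 26.8-29.4%. With the classical O'Brien-Fleming interim p of 0.0088: 33-34%.
- 102 evaluable (51 per arm), 0.016: 56.5%.

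*Printed thresholds (0.016; futility 0.24; final 0.048) at different timings:*

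| Per arm at the look | Efficacy stop | Futility stop | Power | Type I error (28% in both arms) |
|---|---|---|---|---|
| 37 | 0.413 | 0.093 | 0.837 | 0.0494 |
| 38 | 0.428 | 0.097 | 0.836 | 0.0499 |
| 50 | 0.549 | 0.058 | 0.865 | 0.0498 |
| 51 | 0.565 | 0.055 | 0.867 | 0.0500 |

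A half-enrolment look with boundaries of its own (interim 0.0050-0.0056, futility p about 0.35) gives a futility stop of 5.0-5.3% and power of about 0.86.

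*If the printed p-values are two-sided:* power is 0.78 at 51 per arm and 0.72 at 37-38, and the futility stop is 12% and 20%.

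**The case against.** The strongest reply is that the authors meant one look at about 100 patients. Half of 200 is 100, 100/152 = 0.658 rounds to the printed 0.66, and the spend there, 0.0157, rounds to 0.016. On that reading an enrolled count was divided by 152 without allowing for loss, and the paragraphs differ by 2 patients. This is plausible, and it stands against any claim that the half-enrolment sentence is a proven stray. It does not clear the plan: at 25% loss, 100-102 enrolled patients carry information of only 0.49-0.50, so the printed fraction and alpha are then wrong for the look described.

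Second, the 25% covers incomplete follow-up in general, including the 10-14 day call, so loss at 48 hours may be lower. That stands too. It does not follow that the problem fades with lower loss: the gaps of 13 and 2 hold only if enrolment stays at 200, and the plan allows the target to move.

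Third, the futility harm arises only if thresholds from one paragraph are used at the timing of the other. Also, the 27-34% rests on boundaries computed here, because the first paragraph prints none. A different chance of early stopping is not in itself an error. All of this is correct and limits the weight of the point.

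A reader might infer that the conflict inflates type I error. On the one-sided reading with binding futility it does not: the exact error is 4.9-5.0% at each timing computed.

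**Conclusion.** The contradiction is real and should be fixed. At the plan's own 25% loss, the two timings of the single interim are information 0.49 and 0.66, or 100 and about 136 enrolled patients if 102 counts evaluable patients. If 102 counts enrolled patients, the head counts nearly agree, but the printed 0.66 and 0.016 do not fit.

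Only the 36 rests solely on plan figures. At lower loss, the gap depends on an assumed rate and on what happens to the enrolment target.

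Mixing the paragraphs would raise wrongful futility stopping from about 5.5% to 9-10% and lower power from 0.87 to 0.84, on the one-sided reading. It would be too strong to say that power certainly stays above 80%. The second interim paragraph names a one-sided test, but the power statement in 7c uses two-sided 0.05, and the planned chi-squared test usually gives a two-sided p-value. On a two-sided reading, power goes from 0.78 to 0.72. The documents do not settle which applies.

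It would also be too strong to say that the second paragraph is shown to govern. The printed alpha fits its information fraction, but which patients the authors counted remains open.

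**What to change.** State one interim trigger, counted in randomised patients with an evaluable 48-hour outcome, and remove the other timing.

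- To keep the printed 0.66, 0.016 and futility p = 0.24, set the trigger at about 100 evaluable patients. That is about 133 enrolled at 25% loss (100/0.75).
- If 102 evaluable is kept, restate the fraction as 0.67 and the interim spend as 0.0167. That is about 136 enrolled at 25% loss.
- If the look falls at another fraction, compute the efficacy boundary from the spending function at the fraction reached. Rerun the design simulation for the futility value, since the documents name no futility spending function.

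The cost is mainly wording, plus a rerun of the simulation if the fraction changes; sample size is unaffected. The downside is that the look comes later in enrolment than the half-enrolment wording implies, so any early stop comes later too.
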